8.2.3.1 Efficacy Endpoints

Primary Endpoints:

• Change from baseline in A1C at Week 12

Key Secondary Endpoints:

- Change from baseline in body weight at Week 12
- Change from baseline in FPG at Week 12

Other Secondary Endpoints

• Change from baseline and percent change from baseline in fasting lipids (including LDL-cholesterol level, HDL-cholesterol level and triglyceride level) at Week 12 Change from baseline in systolic and diastolic blood pressure at Week 12

Other Endpoints of Interest

- Change from baseline in glucagon receptor activation biomarkers (including ketones, glucagon, FGF-21 and kisspeptin)
- Change from baseline in fasting measures of insulin secretion (HOMA-β) and insulin resistance (HOMA-IR), at Week 12

Protocol/Amendment No.: 004-02

8.2.3.2 Safety Endpoints

Safety and tolerability will be assessed by a clinical review of all relevant adverse experiences and monitoring variables related to blood chemistry, hematology, vital signs, and ECG.

Tier 1 safety endpoints are adverse events of symptomatic hypoglycemia (see Table 13).

Tier 2 safety endpoints include changes from baseline in HR at different time points.

Adverse events (overall summary, specific AEs, and AEs by system organ class) and PDLCs in laboratory and vital signs parameters (including proportion of subjects with HR>100 bpm or HR increase > 30 bpm) will be classified as belonging to "Tier 2" or "Tier 3", based on the number of events observed.

8.2.3.3 Pharmacokinetics Endpoints

 C_{Trough} will be assessed (see Section 4.2.3.3).

8.2.4 Analysis Populations

8.2.4.1 Efficacy Analysis Populations

The Full Analysis Set (FAS) population will serve as the primary population for the analysis of efficacy data in this study. The FAS population includes subjects who take at least one dose of study therapy and have at least one efficacy measurement either at baseline or during the treatment period. Subjects will be included in the treatment group to which they were randomized.

A secondary population for analyzing primary and key secondary efficacy endpoints at Week 12 will be the Per-Protocol (PP) population. All randomized subjects who take at least one dose of study medication, with a measurement at baseline and the time point of interest (Week 12), without the protocol deviations described below will be included in this population.

Protocol deviations used to determine the PP population are not just a repetition of the exclusion and inclusion criteria in the protocol, but a clinical assessment of deviations from the protocol-specified criteria that will either affect or confound the measures of efficacy. The following rules define protocol violators during the trial period of interest (Day 1 through Week 12) and will be used to identify such subjects prior to unblinding. Subjects with any of the following violations will be excluded from the PP population at all time points.

- **Drug compliance:** A subject will be excluded from the PP population due to low compliance if either of the following applies:
 - Compliance assessed by prime therapy records provided by the investigator in the eCRF is <90%.
 - <75% of evaluable trough PK samples have quantifiable concentrations. This
 criterion is applicable only to subjects in the MK-8521 and liraglutide groups.
 

Protocol/Amendment No.: 004-02

Additionally, a site will be deemed to have low compliance and all subjects from that site (including those randomized to the placebo group) will be excluded from the PP population if either of the following applies:

- o For sites with exactly 2 subjects randomized to active groups, both of these subjects have low compliance based on trough PK criterion noted above.
- o For sites with 3 or more subjects randomized to active groups, ≥50% of subjects have low compliance based on the trough PK criterion noted above.
- Use of prohibited medications: The list of prohibited medications can be found in Section 5.5.
 - o If a subject takes any prohibited antihyperglycemic medications after randomization (Visit 3/Day 1) for a total of ≥14 days or ≥7 consecutive days, he/she will be identified as a protocol violator.
 - o A subject with pharmacologic doses of corticosteroid use ≥ 2 consecutive weeks after randomization will be identified as a protocol violator.
- Incorrect double-blind study medications: If a subject receives incorrect double-blind study medication for a total of ≥14 days during the trial period of interest, then he/she will be identified as a protocol violator.
- Subjects who cannot tolerate 0.5 mL/day from Vial D: If a subject does not tolerate the full target dose of 0.5 mL/day MK-8521 from Vial D, he/she will be identified as a protocol violator. This criterion will only be applied to subjects randomized to the MK-8521 300 µg group.

The final determination on protocol deviations, and thereby the composition of the PP population, will be made prior to the final unblinding of the database and will be documented.

An additional secondary population to analyze the efficacy endpoints will be the modified FAS (mFAS). The modified FAS population is a subset of FAS population that excludes sites identified as having low compliance (as described in the drug compliance description for the PP population above).

The number of subjects included in the FAS, PP and mFAS populations may vary across endpoints due to the degree of missing data for each endpoint. Any substantial differences between conclusions based on the FAS, PP population, and mFAS population will be investigated.

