At Visit 2/Week -2, eligible subjects will enter the 2-week, single-blind, placebo run-in period. All subjects (including those subjects who will eventually be randomized to open-label liraglutide) will be dispensed 2 vials/day single-blind investigational product (referred to as Vial A and Vial B (MK-8521 180 µg and MK-8521 300 µg matching placebos, respectively) and instructed to take one injection (0.1 mL) per day from each vial at approximately the same time of day in the morning during the 2-week single-blind placebo period prior to randomization. Subjects should be reminded to withhold single-blind investigational product on the day of Visit 3/ Day 1. Note: Subjects who miss more than one daily dose (i.e., 2 injections on the same day or 2 single injections on separate days) of the placebo run-in medication are ineligible for randomization.

Subjects meeting eligibility for randomization through Visit 3/Day 1, based on the criteria detailed in Section 5.1, will be eligible to enter the double-blind treatment period.

Table 1 Pre-Randomization Management

Regimen at Visit 1/ Screening	Visit 1/Screening A1C Entry Criterion	Subject Management during the Pre- Randomization Period
On metformin monotherapy (≥1000 mg/day) for ≥12 weeks	A1C \geq 7.5% and \leq 10.5% (\geq 58 mmol/mol and \leq 91 mmol/mol)	 Continue metformin at Visit 1 dose throughout the trial. Proceed to Visit 2/Week -2 and initiate placebo run-in as appropriate Randomize at Visit 3 if subject continues to be eligible.
On dual therapy of metformin (≥1000 mg/day for ≥4 weeks) and a second AHA ¹	A1C ≥7.0% and ≤10.0% (≥53 mmol/mol and ≤86 mmol/mol)	 Continue metformin at Visit 1 dose throughout the trial. Discontinue treatment with other AHA at Visit 1A/Washout Proceed to Visit 2/Week -2 after an AHA washout of ≥8 weeks. Initiate placebo run-in as appropriate Randomize at Visit 3 if subject continues to be eligible²

 $^{^{1}}Allowable \ AHAs \ prior \ to \ screening \ (Visit \ 1): DPP-4 \ inhibitors, \ \alpha-glucosidase \ inhibitors, \ sulfonylureas \ and \ glinides.$

Management of Randomized Subjects

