At **Visit 3/Day 1**, subjects who meet enrollment criteria will enter the 12-week treatment period. Subjects will be randomized in a 1:1:1:1 ratio to 1 of 4 treatment groups: (1) MK-8521 300 µg once-daily (QD), (2) MK-8521 180 µg QD, (3) MK-8521 placebo QD, (4) open-label liraglutide 1.8 mg QD. All treatments will be administered with subcutaneous injection. Subjects are to remain on their stable dose of metformin (≥1000 mg/day) while receiving investigational product (blinded or open-label) during the treatment period.

²Randomization requirements include Visit 2 A1C ≥7.5% and ≤10.5% (≥58 mmol/mol and ≤91 mmol/mol)

Protocol/Amendment No.: 004-02

Subjects randomized to either MK-8521 180 μ g or 300 μ g or placebo will have a 2 and 3 step dose escalation regimen, respectively, to achieve the planned study dose (see Table 6, Section 5.2.1.2). Subjects randomized to liraglutide will have a 2 step dose escalation regimen to achieve the planned study dose.

A double-dummy approach will be used in the trial because the volume of MK-8521 administered differs between the 180 μg and 300 μg dose arms. With the double-dummy approach, subjects randomized to MK-8521 or MK-8521 placebo will administer 2 injections each day: 1 injection from **Vial C** containing active MK-8521 180 μg dose or placebo and 1 injection from **Vial D** containing MK-8521 300 μg or placebo. Subjects randomized to the MK-8521 180 μg group will also receive placebo for MK-8521 300 μg ; subjects randomized to the MK-8521 300 μg group will also receive placebo for MK-8521 180 μg ; subjects randomized to placebo will receive placebo for both MK-8521 300 μg and MK-8521 180 μg . Subjects randomized to liraglutide will receive only open-label liraglutide for the duration of the trial.

MK-8521 or MK-8521 Placebo Dosing

For subjects randomized to the MK-8521 300 μ g treatment group, Vial C will contain placebo and Vial D will contain active MK-8521. The starting dose in the MK-8521 300 μ g treatment group will be 60 μ g (0.1 mL from each vial) from Visit 3/Day 1 through Day 6. The dose will then be escalated to 120 μ g (0.2 mL from each vial) from Visit 4/Week 1 through Day 13, to 180 μ g (0.3 mL from each vial) from Visit 5/Week 2 through Day 20, and to the final dose of 300 μ g (0.3 mL from Vial C and 0.5 mL from Vial D) from Visit 6/Week 3 for the remainder of the 12 weeks (approximately 63 days).

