5.2.2 Timing of Dose Administration

On days without a clinic visit, MK-8521 300 μ g, MK-8521 180 μ g, or matching MK-8521 placebo SC injections; or open-label liraglutide will be administered in the morning at approximately the same time each day. Background metformin is to be taken as prescribed by their primary care physician. MK-8521 or matching placebo injections will be administered SC in the abdominal wall. The injection site should be rotated within the abdominal wall area.

On the days of clinic visits, subjects will take their investigational product, as well as background metformin, after all study procedures are completed.

At Visit 2/Week -2, subjects will enter a single-blind placebo run-in period. Subjects will be taught how to self-administer and will be expected to perform self-administration of the single-blind placebo SC injections during the 2-week single-blind placebo run-in period in preparation for the double-blind dosing period.

Subjects who cannot tolerate the 0.5 mL/day dose from **Vial D** may continue on a dose of 0.3 mL/day from each vial.

Subjects who cannot tolerate at least 0.3 mL/day from each vial should be discontinued (See Section 7.1.4.1).

Protocol/Amendment No.: 004-02

At **Visit 3/Day 1,** MK-8521 300 μ g, MK-8521 180 μ g, or matching MK-8521 placebo SC injections, or open-label liraglutide will be administered (see Section 4.2.2.1 for initial doses and Section 5.2.1.2 for dose escalation) by the subject as a witnessed dose after the completion of study procedures. Background metformin should be taken after all study procedures are completed. Investigational site staff should assure that the administration technique is appropriate, and provide additional training on study drug administration, as necessary.

Subjects will be asked to bring the remaining investigational product (used and unused vials/pens) to the clinic for review at each scheduled visit.

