5.5 Concomitant Medications/Vaccinations (Allowed & Prohibited)

Medications or vaccinations specifically prohibited in the exclusion criteria are not allowed during the ongoing trial. If there is a clinical indication for any medication or vaccination specifically prohibited during the trial, discontinuation from trial therapy or vaccination may be required. The investigator should discuss any questions regarding this with the Sponsor Clinical Director. The final decision on any supportive therapy or vaccination rests with the

Protocol/Amendment No.: 004-02

investigator and/or the subject's primary physician. However, the decision to continue the subject on trial therapy or vaccination schedule requires the mutual agreement of the investigator, the Sponsor and the subject.

AHAs taken by the subject at any time prior to Visit 1/Screening, and any other medications taken within 8 weeks of Visit 1/Screening, should be recorded on the appropriate electronic case report form (eCRF). The site may rely on subject report for this information. Concomitant medications taken during the trial must also be recorded. Subjects should be questioned about their use of concomitant medications at the time points indicated in the Trial Flow Chart — Section 6.0. Subjects should be instructed to contact the study investigator before initiating any prescription or non-prescription medications during study participation. If medical necessity requires initiation of a medication prior to discussion with the study investigator, the subject should communicate with the study investigator as soon as possible.

Prohibited Medications

Medications listed below are prohibited while subjects are receiving investigational product during the treatment period (see Section 5.9 - Subject Withdrawal/Discontinuation from Treatment Criteria):

- 1. All Antihyperglycemic Medications: with the exception of background metformin ≥1000 mg/day) and double-blind (MK-8521 or placebo) or open-label (liraglutide) study medication.
- 2. Corticosteroids: Treatment for ≥14 consecutive days or repeated courses of pharmacologic doses of corticosteroids.

Note: Inhaled, nasal, and topical corticosteroids and physiological replacement doses of adrenal steroids are permitted.

3. Weight-loss Medications: Treatment with or initiation of a weight-loss medication (e.g., orlistat, phentermine, topiramate, lorcaserin) is prohibited (see Section 5.1.3).

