7.1.5.4 Screening Visits

7.1.5.4.1 Visit 1/Screening

Subjects will be consented and screened according to **Visit 1/Screening** Inclusion/Exclusion Criteria and will receive a baseline screening number. The subject's medical history and concomitant medications will be reviewed, and vital signs, body weight, and height will be measured. For subjects assessed as eligible to participate in the trial, fasting blood and urine samples will be obtained.

Review of concomitant medications, assessment of vital signs, and adverse event monitoring will be maintained throughout the trial.

For detailed list of **Visit 1/Screening** procedures refer to Trial Flow Chart (**Section 6.0**).

7.1.5.4.2 **Visit 1A/Washout**

Eligible subjects on dual therapy with metformin and a second AHA will begin an 8-week AHA washout period at Visit 1A/Washout and will be scheduled for Visit 2/Week -2. Allowable AHAs for washout are: DPP-4 inhibitors, α-glucosidase inhibitors, sulfonylureas and glinides. Metformin should be continued at the Visit 1/Screening dose throughout the trial.

Subjects' prior/concomitant medications and adverse events will be reviewed. All subjects will (1) have diet/exercise counseling, (2) receive glucose meters and training in performing SMBG, and (3) receive instruction on hypoglycemia symptoms, hypoglycemia management, and completion of the HAL.

Subjects will be instructed to monitor their fingerstick glucose concentrations with a frequency determined appropriate by the investigator (based upon his/her assessment of the subject's glycemic control) with a minimum of two fasting determinations per week.

See sections 5.7.1 and 7.1.1.8.2 and 7.1.1.8.3 for additional information regarding dietary/and exercise counseling, HAL training and SMBG training, respectively.

Protocol/Amendment No.: 004-02

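### The per-protocol rules miss a change in background metformin dose, so the PP analysis of A1C and FPG does not remove a glycemic confounder that the FAS also carries

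*Combined protocol and SAP*

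**What the plan says.** **Metformin requirement.** Table 1 in Section 2.1 instructs, for both entry regimens: "Continue metformin at Visit 1 dose throughout the trial". The text of the same section adds: "Subjects are to remain on their stable dose of metformin (≥1000 mg/day) while receiving investigational product". For subjects entering washout, Section 7.1.5.4.2 repeats: "Metformin should be continued at the Visit 1/Screening dose throughout the trial". The washout row of the flow chart in Section 6.0 also says the dose is not to be altered. Section 5.5 allows adjustment of non-antihyperglycemic therapies only.

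**Prohibited list.** Section 5.5 prohibits all antihyperglycemic medications "with the exception of background metformin ≥1000 mg/day) and double-blind (MK-8521 or placebo) or open-label (liraglutide) study medication".

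**Timing section.** Section 5.2.2 says: "Background metformin is to be taken as prescribed by their primary care physician".

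**PP population.** Section 8.2.4.1 describes the PP deviations as "a clinical assessment of deviations from the protocol-specified criteria that will either affect or confound the measures of efficacy" and then lists the rules that define violators. The antihyperglycemic rule begins "If a subject takes any prohibited antihyperglycemic medications after randomization" and applies from 14 days in total or 7 consecutive days. The other rules cover study-drug compliance, corticosteroids, incorrect double-blind medication and, in the 300 µg group, intolerance of the full Vial D dose.

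**The concern.** This is an add-on trial with metformin as the only permitted background glucose-lowering drug and A1C as the primary endpoint. A sustained change in metformin dose acts directly on A1C and FPG, and is the kind of deviation that the PP principle in Section 8.2.4.1 aims to remove. The plan excludes a subject for a week of any other glucose-lowering drug but does not address a metformin increase of any length.

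Such changes need not be balanced across arms. An increase is plausibly more likely on placebo, and a reduction plausibly more likely in subjects with gastrointestinal intolerance on active drug. Either would narrow the difference from placebo. The documents give no frequencies, so the direction is a clinical expectation and not a documented fact.

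What is at stake is how the PP result is read. Section 8.2.4.1 promises to investigate substantial differences between the FAS, PP and mFAS conclusions, and Section 8.2.9.2 brings PP analyses into the interim review. If PP and FAS agree, a reader may conclude that departures in background therapy did not matter. On this point the PP set cannot show that, because it has not removed them.

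**Working it through.** **Does any rule catch a metformin dose change?** The rules, checked one by one:

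| Rule | Reaches a metformin dose change? |
|---|---|
| PP compliance below 90% on prime therapy records (8.2.4.1) | No. Section 8.2.10 counts a compliant day by injections taken |
| PP trough PK criterion (8.2.4.1) | No. It concerns MK-8521 and liraglutide |
| PP prohibited antihyperglycemics (8.2.4.1 with 5.5) | Not for a raise, nor for a cut that stays at or above 1000 mg/day |
| PP corticosteroids, incorrect double-blind medication, Vial D intolerance (8.2.4.1) | No |
| Discontinuation from treatment (5.9) | Only a condition that contraindicates metformin |
| PP ANCOVA terms (8.2.5.1) | No metformin term |

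**Three cases, reading 8.2.4.1 with 5.5:**

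1. *Raise, for example from 1000 to 2000 mg/day.* The new dose is background metformin of at least 1000 mg/day, so it is exempt, is not a prohibited drug and is not a PP violation.
2. *Cut to a dose still at or above 1000 mg/day.* Same result.
3. *Cut below 1000 mg/day.* Read literally, this falls outside the exemption and could count as a prohibited antihyperglycemic once the duration rule is met. The text does not say so, and the point stays open.

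In cases 1 and 2 the subject departs from Table 1 yet stays in the PP set if the other PP conditions are met. The FAS has no metformin rule, so the subject is there too.

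**Illustrative size.** The plan states no figure on this point, so there is none to reproduce. The documents give neither the frequency of dose changes nor their effect; both are assumed here. Let *f* be the share of placebo subjects with a raise and *e* the extra A1C fall each gains by Week 12, with no change in the other arms:

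Shift in the difference = *f* × *e*; remaining difference = 0.8 − *f* × *e*

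| *f* | *e* | Shift | Remaining difference |
|---|---|---|---|
| 0.05 | 0.3 | 0.015 | 0.785 |
| 0.05 | 0.5 | 0.025 | 0.775 |
| 0.10 | 0.3 | 0.030 | 0.770 |
| 0.10 | 0.5 | 0.050 | 0.750 |
| 0.20 | 0.3 | 0.060 | 0.740 |
| 0.20 | 0.5 | 0.100 | 0.700 |

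**Scale.** Section 8.2.7 gives a 95% CI half-width of 0.52 for A1C. Its inputs (effective n of 35 per arm, SD 1.1) give 1.96 × 1.1 × √(2/35) = 0.515, which agrees. The largest shift in the table, 0.10, is 0.10/0.52 = 19% of that half-width.

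**The case against.** **The protocol already fixes the dose.** Section 2.1, Section 7.1.5.4.2 and the flow chart all do so, and in that light background metformin in Section 5.5 can fairly be read as the fixed dose. A reader might also infer from Section 5.2.2 that the primary care physician may change it. The documents do not support that: the sentence sits in a section on timing of administration and grants no such permission. This stands, and makes a change a departure from protocol. It does not make it a PP violation, because the PP list works through prohibited drugs.

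**Few subjects may be affected.** Confirmed FPG above the Table 7 thresholds (270 mg/dL through Week 6, then 240 mg/dL) leads to discontinuation. Under Section 5.9.1 those subjects then have a discontinuation visit, a 14-day visit and telephone contacts. Most would lack a Week 12 value and leave the PP set that way, although Section 12.4 maps any value from Day 74 onward to Week 12. What remains is off-protocol changes in completers, which the documents do not suggest are common. This stands and limits the size.

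**Stronger readings.** A reader might infer that dilution would make PP weaker than FAS and be misread. That does not follow: the FAS keeps the same subjects, so the dilution is in both sets. A reader might also put the loss at 15% of the planned effect (8/40 × 0.6 = 0.12; 0.12/0.8 = 15%). That stacks a high assumed frequency, confined to placebo, on a high assumed effect. Section 4.2.3.1 says A1C reflects 3 to 4 months of glucose, so a mid-trial raise would show only in part by Week 12.

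**Selection.** Excluding placebo subjects whose metformin was raised removes poor responders on a post-randomization event. This is true, but it applies equally to the existing exclusion for other antihyperglycemics. It is a limit of any PP set.

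**Discretion before unblinding.** The team could rule on metformin when it finalizes the PP set. It could, but nothing is pre-specified, and liraglutide assignment is open-label throughout.

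**Conclusion.** The gap is real and narrow. As written, a subject whose metformin is raised, or cut to a dose still at or above 1000 mg/day, remains in the PP analysis of A1C and FPG despite departing from Table 1. Treatment of a cut below 1000 mg/day is unsettled. The PP analysis therefore does not do, for the background drug, what Section 8.2.4.1 says it is for, and agreement between FAS and PP is weaker reassurance than it appears.

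The size is unknown. Under the assumed inputs it runs from a few hundredths of a percentage point to about 0.1 of A1C, well inside the planned CI half-width. It would be smaller if raises came late, and would partly cancel if they occurred in all arms. The primary FAS cLDA inference, the power figures and the error rate are unaffected, because the PP analysis is secondary. This is a cheap improvement, not a threat to the trial's conclusion.

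**What to change.** Add one rule to the PP violations in Section 8.2.4.1: after randomization, a total daily metformin dose different from the Visit 1 dose for a total of 14 days or more, or for 7 or more consecutive days. This is the duration rule already used there for other antihyperglycemics. Apply it to all arms and identify the subjects before unblinding. As worded, the rule also settles, for the PP set, how a cut below 1000 mg/day is handled. The sponsor may wish to add a minimum size of change so that trivial differences do not exclude subjects.

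Reconcile the metformin wording in Sections 5.2.2 and 5.5 with Table 1 and Section 7.1.5.4.2. Which clinical wording should prevail is for the sponsor to decide.

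The cost is one bullet and a few PP subjects. Sections 5.5 and 7.1.1.5.2 already require concomitant medication to be recorded. The rule assumes that the record includes metformin dose and dates, which should be confirmed.
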